Study Title: Enhancement of motor function after spinal cord injury.

Principal Investigator: [name] P.T., Ph.D.

Co- Investigator: [name] [name], M.D.

Brief Description

Motor function is largely disrupted in veterans with spinal cord injury (SCI). This has tremendous impact in daily-life activities. This study will examine physiological changes in pathways controlling motor function after SCI and novel methods to enhance the recovery of upper and lower extremity motor function by combining non-invasive repetitive brain stimulation with motor training. The repetitive brain stimulation will occur using a wire coil placed over the participants' head. When activated, this coil will generate a magnetic pulse over a specified area of the head. During training, we will monitor muscle activity through the use of surface electrodes. Subjects will perform precision grip and wrist movements. Impairment in hand function is a major problem after stroke, amyotrophic lateral sclerosis, multiple sclerosis, and other motor disorders, therefore, our work may also be relevant for individuals with other lesions of the nervous system.

Objectives: The goals of this study are to examine the physiology of Central Nervous System pathways contributing to the control of upper and lower extremity movements after SCI, and to promote the recovery of extremity movements by using non-invasive brain stimulation and motor training.

A. Specific Aims and Hypothesis:

Aim 1. Neural Control of Movements in SCI and Control Subjects

Investigate physiological mechanisms contributing to the control of hand movements.

Aim 2. Enhance recovery of motor function by using non-invasive repetitive transcranial magnetic stimulation (rTMS)

To accomplish this aim we propose to complete two main experiments. First we will use rTMS to test the hypothesis that *rTMS induced cortical plasticity during movement will enhance voluntary output in hand muscles (as measures by electromyography and Jebsen Taylor Test) after spinal cord injury (Aim 2a)*. Second, we will combine precision grip and wrist training with rTMS to test the hypothesis that *precision grip training outcomes will be enhanced by rTMS induced cortical plasticity (aim 2b)*.

B. Background and Significance to the VA Mission

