Lower Extremity Physiological Examination Components:

Range of Motion (ROM): active ankle and hip ROM will be measured by a motion capture system (Opti Track, V120: Tri camera, NaturalPoint, Inc) in sitting and standing position. In sitting, subjects will be instructed to complete maximal voluntary dorsiflexion for 10 times separated for period of 10 sec of rest. In standing, subjects will be instructed to complete maximal voluntary hip flexion for 10 times separated for period of 10 sec of rest. Trunk movements will be avoided during testing. The motion capture system will also be utilized to measure foot drop and hip flexion. Markers will be positioned on the external line of the mid trunk, hip, knee, external malleolus, and the lateral side of the 5th metatarsophalangeal joint. The elevation of the toe above ground level will be taken as a measure of foot drop. The amplitude of toe elevation will be calculated from the distance between the marker placed on the 5th metatarsophalangeal joint and the ground (Barthélémy et al., 2010). The largest distance between these two points will be determined and will be referred to as the highest toe elevation. The presence or absence of the second toe elevation prior to heel strike will be measured by subtracting the excursion of the malleolus marker from the elevation of the toe. Hip angle will be constructed by using the trunk, hip and knee markers.

Pinch Grip Strength:

Will be assessed bilaterally using load cells that will record the force generated by the subject. Force will be applied by the thumb and index finger and will be recorded in Newtons (N).

Modified Ashworth Scale and Pendulum Test:

Will be used to measure spasticity level in subjects with SCI during soft tissue stretching.
(Modified Ashworth Scale; Bohannon and Smith, 1987)

Phase 3

Experiment 2 (Aim 2b) :

Individuals with SCI and healthy controls will be randomly assigned to two groups: (1) training + rTMS, and (2) training + sham rTMS. Randomization will be the same as described above. Training will be complete in approximately 15 sessions over approximately 3 weeks. In each session, stimulation or sham stimulation (approximately 25 minutes) will be applied during precision grip and wrist visuo-motor training (approximately 1 hour).

Training + rTMS group- Training will consist of executing three different grip forces with one hand and simultaneously wrist flexion and extension movements while the contralateral hand is at rest.

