Subjects will be instructed to follow a target line on a computer screen as accurately as possible while performing precision grips with simultaneously maximal wrist flexion and extension. Stimulation will be triggered if both movements are performed. See Experiment 1 for rTMS parameters. At each time three targets will be presented separated by approximately 2 seconds of reset on the screen for a total duration of 10 seconds. The period of stimulation will last approximately 24 minutes. Subjects will be randomly assigned to two groups: training + rTMS, and training + sham rTMS. A train of rTMS will be applied during each of the target presentations. The coil will be positioned over the optimal scalp position for activating finger and wrist muscles. Here, 5 pulses at 5 hz will be applied each time that a target appears on the computer screen. In a control task individuals will be asked to perform to follow the same cursor using their lower limb muscles. A total of 1200 rTMS pulses will be applied at 80% of AMT intensity (see more details about rTMS application in AIM 2a).

Training+sham rTMS group- Training will be conducted as described above. For sham rTMS, TMS coil will be positioned in the same location as described above. A second coil will be placed behind the subjects head, and it will discharge in the air using the same stimulation parameters that will be used in the TMS application. During sham stimulation only the coil located behind the subjects head will be triggered. Participants may feel small pressure from the coil positioned on top of their head and hear the click sound during triggering.

Measurements before and after rTMS protocols:

Physiology- We will examine: (a) MEPs, SICI, IHI, and F-wave (See procedures in Aim 1). Precision grip motor performance: We will quantify the following outcomes: (a) Force onset [the time point at which force increases 2SD above force baseline], (b) Force rate (maximum derivative of force (force/s) between force onset and target force), (c) Force area (area between force onset and force decay to zero), and (d) Total force duration (time between force onset and force decay to zero).

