Screening Interview: Identifiable information collected during either the screening interview will be destroyed if the potential subject does not qualify. If the subject does qualify and ultimately enrolls into this research, all information collected will become part of their research record. All security precautions that are reflected in this protocol will apply.

Data Collection and Storage: Research records will be retained in accordance with the Veterans Health Administration (VHA) Records Control Schedule. The Federal Privacy Act protects the confidentiality of medical records. Electronically-stored medical information collected from study participants will be kept on a VA server. Electronic data recorded during experimental sessions will be kept on fully-secured computers (password protected) on a VA server. Unique subject identifiers (i.e., a code accessible only to the PI and AI) will be used to label all electronic data files.

F. Sample Size

Up to 500 participants (250 SCI, and 250 control subjects) will be recruited to participate in this study at the VAMHS and at the University of Miami. Based on our previous protocols testing spinal cord injured subjects and healthy control subjects, we have added a 25% attrition rate to the number of subjects we plan to enroll in the study.

All participants will be between 18 and 85 years of age. We plan to recruit both veterans and non-veterans.

G. Data analysis is consistent with the study objective

Aim 1: Repeated-measures ANOVA and Tukey post hoc test will be used to assess the effect of TASK (rest, precision grip/wrist flexion, and precision grip/wrist extension) and GROUP (SCI, controls) on physiological measurements.

Aim 2a: Repeated measures ANOVA and Tukey post hoc test will be used to determine the effect of TIME (0,10, 30, 60 min after a single rTMS session), STIMULATION (rTMS, sham rTMS over control brain area) on physiological and behavioral measurements.

Aim 2b: repeated measures of ANOVA and Tukey post hoc analysis will be used to determine effects of GROUP (training + rTMS, training + sham rTMS), TIME (sessions number 1,5,10 and follow up 1,2, and 3 months) on physiological outcomes and motor performance.

H. Privacy and Confidentiality:

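### Aim 2b randomises SCI participants and healthy controls to the same two arms, but its ANOVA has no population factor, so as written no Aim 2b test isolates the rTMS effect after SCI

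*Combined protocol and SAP*

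**What the plan says.** - **Who is randomised.** The description of the Aim 2b training experiment under Phase 3 states: "Individuals with SCI and healthy controls will be randomly assigned to two groups: (1) training + rTMS, and (2) training + sham rTMS". Allocation uses the envelope lottery described for Experiment 1; no strata are mentioned.
- **How Aim 2b is analysed.** Section G, Aim 2b: repeated-measures ANOVA with Tukey post hoc tests to "determine effects of GROUP (training + rTMS, training + sham rTMS") and of TIME (sessions 1, 5 and 10, then follow-up at 1, 2 and 3 months). The outcomes are physiological measures and motor performance.
- **How Aim 1 is analysed.** Section G, Aim 1 tests TASK and "GROUP (SCI, controls) on physiological measurements". The label GROUP therefore means population in Aim 1 and treatment arm in Aim 2b.
- **What the study is for.** The Objectives are to study pathways controlling "upper and lower extremity movements after SCI, and to promote the recovery of extremity movements by using non-invasive brain stimulation" with motor training.
- **The hypotheses.** Aim 2b says that "precision grip training outcomes will be enhanced by rTMS induced cortical plasticity (aim 2b") and names no population. Aim 2a does name one: "as measures by electromyography and Jebsen Taylor Test) after spinal cord injury (Aim 2a").
- **Numbers.** Section F: "Up to 500 participants (250 SCI, and 250 control subjects) will be recruited to participate in this study". This is a ceiling for the whole study; Aim 2b has no figure of its own.

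**The concern.** The Aim 2b model has 2 arms × 6 times = 12 cells, and each cell mixes injured and uninjured people. Every arm effect, arm-by-time effect and Tukey contrast between arms is therefore an average over two populations. It equals the SCI effect only if rTMS works equally well in both, and the listed factors cannot test that.

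The plan does not claim equal response, and the Inclusion Criteria give reason to doubt it: controls must have full wrist movement on both sides, whereas SCI participants need only a little. The Aim 2b performance outcomes (force onset, rate, area and duration) can be measured in both populations, so nothing in the outcome list keeps controls out of the ANOVA.

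The error can go either way. If controls respond less, the pooled result understates the SCI effect. If only controls respond, it can be significant with no SCI benefit. If the choice between pooled and SCI-only analysis stays unwritten, it can also be made after the results are seen.

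**Working it through.** **The plan's own figure.** The total of 500 cannot be reproduced. With the 25% attrition allowance it fits 375 / 0.75 or 400 × 1.25, but neither base appears in the document. No alpha, power, effect, SD or sample size is given for Aim 2b.

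**What the stated model estimates.** With w the SCI share:

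pooled effect = w × (SCI effect) + (1 − w) × (control effect)

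**Assumed inputs** (none from the plan): 50 SCI + 50 controls per arm, outcome SD 1 in both populations, before–after correlation 0.7, SCI effect 0.5 SD, same mean change under sham in both populations, two-sided 5% t-test on change scores. The SD of change is √(2 × (1 − 0.7)) = √0.6 = 0.775.

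**SCI only.** SE = 0.775 × √(2/50) = 0.155; 0.5 / 0.155 = 3.23; power 89%.

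**Pooled, controls gain nothing.** The effect is 0.5 × 0.5 + 0.5 × 0 = 0.25. Mixing two means in the rTMS arm adds 0.5 × 0.5 × 0.5² = 0.0625 to its variance. SE = √((0.6625 + 0.6)/100) = 0.112; 0.25 / 0.112 = 2.23; power 60%.

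Simulation (20,000 to 40,000 runs per setting) agrees:

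| SCI effect | Control effect | Pooled test significant | SCI-only test significant |
|---|---|---|---|
| 0.5 | 0 | 60% | 89% |
| 0.5 | 0.25 | 92–93% | 89% |
| 0.5 | 0.5 | over 99% | 89% |
| 0 | 0.5 | 60% | 5% |
| 0 | 0.25 | 20% | 5% |

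If controls vary less (SD 0.3 of the SCI SD) and only they gain, by half of their own SD, the pooled test is significant 15% of the time.

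**Other mixes per arm:**

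| SCI + controls | Power if only SCI gain 0.5: pooled / SCI-only | Pooled test significant if only controls gain 0.5 |
|---|---|---|
| 30 + 70 | 26% / 69% | 88% |
| 70 + 30 | 88% / 97% | 26% |
| 20 + 20 | 28% / 51% | 28% |

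**When pooling helps.** Let r be the control effect divided by the SCI effect. Pooling doubles the sample (a gain of √2) but multiplies the effect by (1 + r)/2. Break-even is (1 + r)/2 × √2 = 1, so r = 0.41. This needs equal numbers, equal SDs and equal mean change under sham.

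**Six-time-point GROUP × TIME test.** The assumed arm effect is zero at session 1, half at session 5 and full from session 10, with compound symmetry 0.7. If controls gain nothing, power is about 62% pooled against 92–93% SCI-only. If only controls gain 0.5 SD, the pooled test is significant about 62% of the time. The change-score picture carries over.

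**The case against.** **Separate analyses may have been intended.** Section G gives one short sentence per aim and never defines an analysis set, so separate ANOVAs for SCI and controls fit the text as well as pooling does. This stands: the document does not show that pooling will happen, and the percentages apply only if it does. But the plan names population for Aim 1 and not here, and nothing else in it settles the question.

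**The Aim 2b hypothesis is population-neutral.** True; the SCI target is taken from the title and the Objectives. Even under a general hypothesis, a pooled result does not answer the SCI objective.

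**SCI-specific measures are collected.** The SCIM self-care subscale and CUE are recorded around Aim 2b training and at follow-up. The Aim 2b ANOVA line covers only physiological outcomes and motor performance, so they provide no planned SCI test.

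**The illustration assumes equal mean change under sham.** Correct, and it matters for the break-even. If controls change 0.5 SD less under sham, pooled power is 53% when they gain nothing and about 90% when they gain half, with break-even near 52%. At 1 SD less, the figures are 39% and 84%, with break-even near 71%. In this direction the base case flatters the pooled test. The rate of significance when only controls gain moves less (60% and 53%).

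**Conclusion.** The concern holds, with high confidence on structure: both populations are randomised, the listed factors are arm and TIME only, and no analysis set is stated. Run as written on everyone randomised, Aim 2b has no test that isolates the rTMS effect after SCI.

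The size is illustrative. In the assumed base case, pooling costs about 29 points of power (89% to 60%) if controls gain nothing, and gives a significant result about 60% of the time if controls alone gain 0.5 SD. It helps if controls respond nearly as well as SCI participants, but the stated model could not show that they did. The trial remains analysable, so this should be fixed but is not fatal.

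**What to change.** 1. State who enters the Aim 2b ANOVA. If separate ANOVAs are intended, say so and say which one answers Aim 2b.
2. Otherwise add POPULATION (SCI, control) and its interactions with GROUP and TIME: four terms (POPULATION, POPULATION × GROUP, POPULATION × TIME, and the three-way term) on a variable already recorded.
3. Prespecify rTMS minus sham over TIME within SCI as the contrast that answers the recovery objective, and report controls separately.
4. Test that contrast with the SCI participants' own residual variance, by an SCI-only ANOVA or population-specific variances. With one common residual, its type I error on change scores is about 9%, 12% or 15% if the control SD is 0.7, 0.5 or 0.3 of the SCI SD. For example, at 0.3 the SE is understated by √((1 + 0.09)/2) = 0.738, so the effective critical value is 1.96 × 0.738 = 1.45. For the six-time-point GROUP × TIME test at 0.3 it is about 30%.
5. Optionally, draw allocations separately for SCI and controls; this mainly protects the GROUP main effect.

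**Cost.** One clarifying sentence, a few model terms and one contrast. The SCI contrast uses fewer people and loses power if controls respond similarly: in the base case 89% against 92–93% if they gain half as much, and against over 99% if they gain equally. Its adequacy cannot be judged until an Aim 2b number is stated; 80% power at 0.5 SD needs 39 SCI participants per arm at correlation 0.7 and 64 at correlation 0.5. The population-by-arm interaction has only about 62% power in the base case with no control gain (0.5 / √(4 × 0.6/50) = 2.28), so treat it as supportive.

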(B). Motoneuronal excitability (reflected by F-wave persistence and amplitude): F-waves will be tested by using supra-maximum stimulus intensity (120% of the maximal motor response) to the ulnar nerve at the wrist and the median nerve at the elbow. The anode and cathode will be approximately 3 cm apart and 1 cm in diameter. We will examine F-waves in first dorsal interosseous, flexor and extensor carpis radialis muscles.

Phase 2

Aim 2a. Enhance recovery of motor function by using non-invasive repetitive transcranial magnetic stimulation (rTMS)

To accomplish this aim we propose to complete two main experiments. First we will use rTMS to test the hypothesis that *rTMS induced cortical plasticity during movement will enhance voluntary output in hand muscles (as measures by electromyography and Jebsen Taylor Test) after spinal cord injury (Aim 2a)*. Second, we will combine precision grip and wrist training with rTMS to test the hypothesis that *precision grip training outcomes will be enhanced by rTMS induced cortical plasticity (aim 2b)*.

Experiment 1 (Aim 2a)

Participants will be randomly assigned to three groups: (1) rTMS, (2) Sham rTMS and (3) sham rTMS over control brain area. Randomization will be performed by lottery (i.e. Drawing from an envelope a piece of paper indicating the intervention). In the first two groups, rTMS stimulation will be targeting finger and wrist muscles during precision grip and write voluntary contractions. In the last group, rTMS will be applied over the dorsolateral prefrontal cortex (DLPFC) or at the leg presentation of the primary motor cortex, or at other related control area as needed. Each subject will be asked to participate in all sessions separated by a washout period of approximately one week. During testing, subjects will be seated in an armchair with both arms flexed at the elbow by 90 degrees. In each group we will use the same apparatus described in Aim1. At the start of the experiment subjects will perform 3 brief MVCs (3-5s) into index finger abduction and wrists flexion and extension, separated by 30 seconds. The maximal forces will be used to set targets for subsequent submaximal contractions.

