Motor function- We will use range of motion (ROM), JTT, Pinch force, Chedoke arm and Hand inventory, and sensory function of the upper and lower extremities using the American Spinal Injury Association (ASIA) sensory scores and Electrical Perceptual Threshold (EPT). These functional and sensory tests are described in detail in Aim 2a.

Plan for multiple rTMS sessions using Brainsight for MRI co-registration: to ensure that the same area of the motor cortex is stimulated during multiple rTMS sessions we will use the Brainsight co-registration system. We will use an MRI scanner located at the University of Miami Applebaum MRI center or at the Miami VA Medical center. Individuals will be asked to participate in the scan session at their convenience as soon as they are enrolled in Aim 1 of this proposal. Individuals who only participate in Aim 2 of the study will be asked to have the MRI session after they have signed the consent form.

Plan for assessment of long-term effects of rTMS: Physiological and behavioral measurements will be acquired before and after sessions 1,5, and 10.

Phase 3- Follow up

Follow up measurements will be taken after 1, 2, and 3 months after Phase 3 testing to measure any sustained improvements in hand function. This assessment will be completed in a single session. These assessments will be the same as in Phase 1-3 of this research study. Each session will last about 1 hour.

Physiological measurements- We will examine MEPs, SICI, IHI, and F-waves (see procedures in Aim1). Precision Grip motor performance: we will examine Force onset, rate, area and total force duration (see procedures in Aim 2a.) Hand motor function: we will examine JTT, Pinch force, Chedoke Arm and Hand inventory, and sensory function of the hand using the American Spinal Injury Association (ASIA) sensory scores (see procedures in Aim 2a).

Assessment of quality of life and functional independence after SCI- the following measurements will be conducted before and after training sessions in Aim 2B, and at the follow up visits 1,2, and 3 months after training.

- (a) Self-care subscale of the spinal cord independence measure- Version III (SCIM; itzkovich et al., 2007)
- (b) The Capabilities of upper Extremities (CUE; Marino et al., 1998)

Demographics will be collected in all subjects. This will include variables such as age, gender, race, height, weight, and veteran status. For individuals with SCI, we will also collect level of injury and date of injury.

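### Section G names only GROUP and TIME effects for Aim 2b, not the between-arm comparison of gain that the hypothesis calls for

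*Combined protocol and SAP*

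**What the plan says.** The Specific Aims state the Aim 2b hypothesis as "precision grip training outcomes will be enhanced by rTMS induced cortical plasticity (aim 2b"), and the Phase 2 text repeats it. Under Experiment 2 (Aim 2b), "Individuals with SCI and healthy controls will be randomly assigned to two groups: (1) training + rTMS, and (2) training + sham rTMS". The two arms differ only in real or sham stimulation; for the sham arm, "Training will be conducted as described above". On the amount of training: "Training will be complete in approximately 15 sessions over approximately 3 weeks".

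The whole analysis text for Aim 2b is one sentence in section G, which uses a repeated-measures ANOVA with Tukey post hoc tests to "determine effects of GROUP (training + rTMS, training + sham rTMS), TIME (sessions number 1,5,10 and follow up 1,2, and 3 months"). GROUP thus has two levels and TIME six. The documents contain no GROUP x TIME term, change-from-baseline contrast or baseline covariate for this aim.

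The plan for long-term effects of rTMS says "Physiological and behavioral measurements will be acquired before and after sessions 1,5, and 10". A pre-session-1 measurement is therefore collected, but section G does not say whether the before or the after value is the session 1 level of TIME. The follow-up visits are there "to measure any sustained improvements in hand function".

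**The concern.** The hypothesis is about a difference in gain: does training + rTMS improve people more than training + sham? Neither named effect is built to answer that.

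- **TIME** averages over the arms. Its null is that nothing changes across sessions and follow-up. No arm is untrained, so that null is false whenever training or repeated testing helps, even if rTMS adds nothing.
- **GROUP** averages over all six times. It does compare rTMS with sham, but it counts session 1 as an outcome, when at most one of about 15 training sessions has been given. It also carries the full between-person variance, because no baseline is used.

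GROUP, TIME, any interaction the software prints and a set of Tukey pairs will all be available. The plan does not say which of them decides whether rTMS works, or what would count as a sustained benefit of rTMS.

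**Working it through.** **Inputs from the documents.** Two randomised arms, both trained; six TIME levels; a measurement before session 1. Section F gives a ceiling of 500 (250 + 250) for the whole study, with 25% attrition. It gives no Aim 2b number, power, effect size, SD or correlation, so there is no planned Aim 2b figure to reproduce.

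**Assumptions.** Two-sided alpha 0.05; SD 1; equal correlation rho between all times; n per arm. Power is from the noncentral F distribution.

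**Step 1: TIME when rTMS does nothing.** Let both arms gain g x (0, 0.4, 0.8, 1, 1, 1). The sum of squares of that shape about its mean is 0.86. Noncentrality = 2n x 0.86 x g² / (1 − rho). For g = 0.3, n = 20, rho = 0.6: 40 x 0.86 x 0.09 / 0.4 = 7.74, so TIME rejects 53% of the time. At 10, 20, 40 and 100 per arm the rates are 27%, 53%, 87% and 100%; for g = 0.5 they are 68%, 96%, 100% and 100%. In 4,000 simulated trials with no rTMS effect (n = 30, rho = 0.7, gain 0.5 SD), TIME rejected 100%, GROUP 5.4% and GROUP x TIME 4.8%.

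**Step 2: dilution of GROUP.** If session 1 is the pre-session value and rTMS adds a constant d afterwards, GROUP estimates (0 + 5d)/6. An effect of 0.50 SD becomes 0.417 SD, a loss of 1/6. At n = 30 and rho = 0.7, GROUP has 45% power, against 59% if session 1 is left out. If session 1 is instead the post-session value, with 30% of the effect there and 60% at session 5, the averages are 0.408 SD with session 1 and 0.460 SD without it, a loss of 11%.

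**Step 3: three between-arm tests.** Let d_j be the rTMS effect at time j, and m the mean of the five later d_j.

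- GROUP: noncentrality (n/2) x (mean d)² / [(1 + 5rho)/6], df 1 and 2n − 2.
- GROUP x TIME, omnibus: (n/2) x sum(d_j − mean d)² / (1 − rho), df 5 and 5(2n − 2).
- Mean of the later times adjusted for the pre-session-1 value: (n/2) x m² / [(1 + 4rho)/5 − rho²], df 1 and 2n − 3.

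Profile A is 0, 0.25, 0.5, 0.4, 0.3, 0.2 SD (mean 0.275, m = 0.33). Profile B is 0, 0.2, 0.4, 0.5, 0.5, 0.5 SD (mean 0.35, m = 0.42). Worked case, A at rho = 0.3 and n = 40: GROUP 20 x 0.0756/0.4167 = 3.63, power 47%; adjusted 20 x 0.1089/0.35 = 6.22, power 69%.

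Power at 40 per arm:

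| rho | A: GROUP | A: GROUP x TIME | A: adjusted | B: GROUP | B: GROUP x TIME | B: adjusted |
|---|---|---|---|---|---|---|
| 0.3 | 47% | 31% | 69% | 67% | 44% | 88% |
| 0.4 | 40% | 35% | 68% | 59% | 50% | 87% |
| 0.5 | 36% | 42% | 69% | 53% | 59% | 88% |
| 0.6 | 32% | 52% | 73% | 47% | 71% | 91% |

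The order of GROUP and the omnibus interaction reverses between rho 0.4 and 0.5 in these profiles. With a constant later effect, GROUP is still ahead at rho = 0.5 (55% against 44% at n = 30).

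**Step 4: why the adjusted comparison stays ahead.** With no rTMS effect at session 1, mean d = 5m/6. Because (1 + 4rho)/5 − rho² = (1 − rho)(1 + 5rho)/5, the ratio of the adjusted noncentrality to that of GROUP is 1.2/(1 − rho), whatever the later profile. That is 1.7 at rho = 0.3 and 3.0 at rho = 0.6.

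The gain does not depend on session 1 being the pre-session value. In the post-session scenario of Step 2 (n = 40, rho = 0.6), GROUP has 60% power and GROUP x TIME 40%. Adjusting the later times for the pre-session-1 value gives 20 x 0.46²/0.32 = 13.2, about 95%.

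**The case against.** Four points can fairly be made for the plan.

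1. GROUP is a correct test. Arms are randomised, so it rejects at 5% when rTMS does nothing, and comparing the two arms is a legitimate reading of the hypothesis. This stands: the objection to GROUP is efficiency, not validity.
2. Listing the factors of a repeated-measures ANOVA is common shorthand for the factorial model, and software usually prints the interaction. This stands in part. A printed term is not a pre-specified one, and the sentence still does not say which result decides.
3. A reader might infer that the sponsor means to present TIME as an rTMS effect, because the long-term-effects paragraph and the follow-up purpose do not mention sham. The documents do not support that. Those passages describe a visit schedule and a purpose, while section G covers the same sessions and follow-ups with sham as a level of GROUP. The plan leaves the misreading open but does not commit to it.
4. A reader might infer that GROUP x TIME is simply the more powerful test and that naming it is enough. That is not supported either. The ranking depends on a correlation the documents do not give, and at low correlation the 5-df interaction is the weaker test.

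**Conclusion.** The point holds as a gap in the specified analysis that has a better and nearly free alternative. The hypothesis calls for a between-arm comparison of gain, and section G does not name one. TIME cannot speak to rTMS. It does not always reject when training works (27% in the smallest case in Step 1), but when it rejects, it does so for reasons shared by both arms. GROUP is valid but loses up to 1/6 of a constant later effect and ignores the baseline.

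The baseline-adjusted comparison beat GROUP in every case run: profiles A, B and a constant later effect, rho 0.3 to 0.8, 20 to 60 per arm. The percentages rest on assumed n, SD, effect profile and equal correlation, so they show direction and rough size, not the power of this trial. No general advantage of the omnibus interaction over GROUP is claimed.

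**What to change.** Replace the Aim 2b sentence in section G with text to this effect:

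> The effect of rTMS in Aim 2b is the difference between training + rTMS and training + sham at sessions 5 and 10 and at 1, 2 and 3 months, adjusted for the pre-session-1 value as a covariate and reported with a 95% CI. One contrast, either the average over these later times or one stated time, is the deciding test. Sustained benefit of rTMS means the adjusted between-arm difference at 1, 2 and 3 months. The TIME main effect and within-arm Tukey comparisons describe training and practice and will not be used to conclude anything about rTMS.

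The text should also say whether the before or the after measurement is used at sessions 5 and 10. The post-session-1 value should not serve as the covariate, because it may already contain some rTMS effect.

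The cost is a slightly longer analysis section, with no new visits, measurements or participants. The sponsor gives up only the option of citing a TIME effect as evidence for rTMS.
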